10.3 Expedited Adverse Event Reporting

10.3.1 Rave-CTEP-AERS Integration

The Cancer Therapy Evaluation Program Adverse Event Reporting System (CTEP-AERS) integration enables evaluation of post-baseline AEs entered in Rave to determine whether they require expedited reporting, and facilitates entry in CTEP-AERS for those AEs requiring expedited reporting.

All AEs that occur after baseline are collected in Medidata Rave using the Adverse Event form, which is available for entry at each treatment or reporting period, and used to collect AEs that start during the period or persist from the previous reporting period. The Clinical Research Associate (CRA) will enter AEs that occur prior to the start of treatment on a baseline form that is not included in the Rave-CTEP-AERS integration. AEs that occur prior to enrollment must begin and end on the baseline Adverse Event form and should not be included on the standard Adverse Events form that is available at treatment unless there has been an increase in grade.

Prior to sending AEs through the rules evaluation process, site staff should verify the following on the Adverse Event form in Rave:

- The reporting period (course/cycle) is correct, and
- AEs are recorded and complete (no missing fields) and the form is query-free (fields added to the form during study build do not need to be query-free for the integration call with CTEP-AERS to be a success).

The CRA reports AEs in Rave at the time the Investigator learns of the event. If the CRA modifies an AE, it must be re-submitted for rules evaluation.

Upon completion of AE entry in Medidata Rave, the CRA submits the AE for rules evaluation by completing the Expedited Reporting Evaluation form. Both NCI and

protocol-specific reporting rules evaluate the AEs submitted for expedited reporting. A report is initiated in CTEP-AERS using information entered in Medidata Rave for AEs that meet reporting requirements. The CRA completes the report by accessing CTEP-AERS via a direct link on the Medidata Rave Expedited Reporting Evaluation form.

In the rare occurrence that Internet connectivity is lost, a 24-hour notification is to be made to CTEP by telephone at [contact]. Once Internet connectivity is restored, the 24-hour notification that was phoned in must be entered immediately into CTEP-AERS using the deep link from Medidata Rave.

Additional information about the CTEP-AERS integration is available on the CTSU website:

- Study specific documents: Protocols > Documents > Education and Promotion, and
- Expedited Safety Reporting Rules Evaluation user guide: Resources > CTSU Operations Information > User Guides.

NCI requirements for SAE reporting are available on the CTEP website:

- NCI Guidelines for Investigators: Adverse Event Reporting Requirements is available at https://ctep.cancer.gov/protocolDevelopment/electronic_applications/docs/aeguidelines.pdf.

10.3.2 Distribution of Adverse Event Reports

CTEP-AERS is programmed for automatic electronic distribution of reports to the following individuals: Principal Investigator and Adverse Event Coordinator(s) (if applicable) of the Corresponding Organization or Lead Organization, the local treating physician, and the Reporter and Submitter. CTEP-AERS provides a copy feature for other e-mail recipients.

10.3.3 Expedited Reporting Guidelines

Use the NCI protocol number and the protocol-specific patient ID assigned during trial registration on all reports.

Note: A death on study requires both routine and expedited reporting, regardless of causality as long as the death occurred within 30 days after the last administration of the investigational agent. Attribution to treatment or other cause must be provided.

Death due to progressive disease should be reported as **Grade 5 “Disease progression”** in the system organ class (SOC) “General disorders and administration site conditions.” Evidence that

the death was a manifestation of underlying disease (e.g., radiological changes suggesting tumor growth or progression; clinical deterioration associated with a disease process) should be submitted.

Phase 1 and Early Phase 2 Studies: Expedited Reporting Requirements for Adverse Events that Occur on Studies under an IND/IDE within 30 Days of the Last Administration of the Investigational Agent/Intervention ^{1,2}

FDA REPORTING REQUIREMENTS FOR SERIOUS ADVERSE EVENTS (21 CFR Part 312)

NOTE: Investigators **MUST** immediately report to the sponsor (NCI) **ANY** SAEs, whether or not they are considered related to the investigational agent(s)/intervention (21 CFR 312.64).

An AE is considered serious if it results in **ANY** of the following outcomes:

- 1) Death
- 2) A life-threatening AE
- 3) An AE that results in inpatient hospitalization or prolongation of existing hospitalization for \geq 24 hours.
- 4) A persistent or significant incapacity or substantial disruption of the ability to conduct normal life functions
- 5) A congenital anomaly/birth defect.
- 6) Important Medical Events (IME) that may not result in death, be life threatening, or require hospitalization may be considered serious when, based upon medical judgment, they may jeopardize the patient or subject and may require medical or surgical intervention to prevent one of the outcomes listed in this definition. (FDA, 21 CFR 312.32; ICH E2A and ICH E6).

ALL SAEs that meet the above criteria **MUST** be immediately reported to the NCI via CTEP-AERS within the timeframes detailed in the table below.

Grade 1-2 Timeframes	Grade 3-5 Timeframes
24-Hour notification, 10 Calendar Days	24-Hour notification, 5 Calendar Days

NOTE: Protocol-specific exceptions to expedited reporting of SAEs are found in the Specific Protocol Exceptions to Expedited Reporting (SPEER) portion of the CAEPR.

Expedited AE reporting timeframes are defined as:

- “24-Hour notification, 5 Calendar Days” - The SAE must initially be reported via CTEP-AERS within 24 hours of learning of the SAE, followed by a complete expedited report within 5 calendar days of the initial 24-hour report.
- “24-Hour notification, 10 Calendar Days” - The SAE must initially be reported via CTEP-AERS within 24 hours of learning of the SAE, followed by a complete expedited report within 10 calendar days of the initial 24-hour report.

¹SAEs that occur more than 30 days after the last administration of investigational agent/intervention and have an attribution of possible, probable, or definite require reporting as follows:

Expedited 24-Hour notifications are required for all SAEs followed by a complete report

- Within 5 calendar days for Grade 3-5 SAEs
- Within 10 calendar days for Grade 1-2 SAEs

²For studies using nuclear medicine or molecular imaging IND agents (NM, SPECT, or PET), the SAE reporting period is limited to 10 radioactive half-lives, rounded UP to the nearest whole day, after the agent/intervention was last administered. Footnote “1” above applies after this reporting period.

10.4 Routine Adverse Event Reporting

All Adverse Events **must** be reported in routine study data submissions. **AEs reported expeditiously through CTEP-AERS must also be reported in routine study data submissions.**

Adverse event data collection and reporting, which are required as part of every clinical trial, are done to ensure the safety of patients enrolled in the studies as well as those who will enroll in future studies using similar agents. AEs are reported in a routine manner at scheduled times during the trial using Medidata Rave. For this trial the Adverse Event CRF is used for routine AE reporting in Rave.

10.5 Pregnancy

Although not an adverse event in and of itself, pregnancy as well as its outcome must be documented via **CTEP-AERS**. In addition, the ***Pregnancy Information Form*** included within the NCI Guidelines for Adverse Event Reporting Requirements must be completed and submitted to CTEP. Any pregnancy occurring in a patient or patient's partner from the time of consent to 90 days after the last dose of study drug must be reported and then followed for outcome. Newborn infants should be followed until 30 days old. Please see the "NCI Guidelines for Investigators: Adverse Event Reporting Requirements for DCTD (CTEP and CIP) and DCP INDs and IDEs" (at http://ctep.cancer.gov/protocolDevelopment/adverse_effects.htm) for more details on how to report pregnancy and its outcome to CTEP.

10.6 Secondary Malignancy

A *secondary malignancy* is a cancer caused by treatment for a previous malignancy (e.g., treatment with investigational agent/intervention, radiation or chemotherapy). A secondary malignancy is not considered a metastasis of the initial neoplasm.

CTEP requires all secondary malignancies that occur following treatment with an agent under an NCI IND/IDE be reported expeditiously via CTEP-AERS. Three options are available to describe the event:

- Leukemia secondary to oncology chemotherapy (e.g., acute myelocytic leukemia [AML])
- Myelodysplastic syndrome (MDS)
- Treatment-related secondary malignancy

Any malignancy possibly related to cancer treatment (including AML/MDS) should also be reported via the routine reporting mechanisms outlined in each protocol.

10.7 Second Malignancy

A second malignancy is one unrelated to the treatment of a prior malignancy (and is **NOT** a metastasis from the initial malignancy). Second malignancies require **ONLY** routine AE reporting unless otherwise specified.

11. STUDY CALENDAR

	Pre-Treatment Screening ^L	Cycle 1 ^M				Cycle 2 ^M				Cycle 3+ ^M				Off Study ^N
		Wk 1	Wk 2	Wk 3	Wk 4	Wk 1	Wk 2	Wk 3	Wk 4	Wk 1	Wk 2	Wk 3	Wk 4	
Belinostat^A		X				X				X				
SGI-110 (guadecitabine) or ASTX727^A		X				X				X				
Informed consent	X													
Demographics	X													
Medical history	X													
Concurrent meds	X	X				X				X				X
Physical exam ^B	X	X		X		X				X				X
Vital signs ^C	X	X		X		X				X				X
Height	X													X
Weight	X	X				X				X				X
Performance status	X													
CBC ^D	X	X		X		X		X		X				X
Serum chemistry ^E	X	X		X		X		X		X				X
Coagulation ^F	X													X
Pregnancy test ^G	X													X
ECG ^H	X													X
Adverse events		Throughout study												X
Pill Diary		X				X				X				X
Imaging evaluation of disease status ^I	X									X				X
Tumor biopsy for research correlates ^J	X					X								
Blood collection for research correlates ^K	X													

^A Belinostat: 1000 mg/m² IV on days 1-5 of each 28 day cycle; SGI-110 (guadecitabine): 45 mg/m² SC on days 1-5 of each 28 day cycle; ASTX727: cedazuridine 100 mg/decitabine 35 mg PO on days 1-5 of each 28 day cycle.

Patients will be instructed to bring the pill bottle for ASTX727 to clinic where they will take the drug. Patients are assessed by the treating investigator on day 1 of each cycle. During cycle 1, an additional clinic assessment occurs at week 3, day 1 (\pm 3 days). Dosing window of \pm 3 days is allowed; however, both agents must begin dosing on the same day.

^B A complete physical exam is performed at screening and end of study. A limited, symptom based physical exam is performed at other timepoints.

^C Vital signs include measurements of temperature, heart rate, blood pressure, respiratory rate, and oxygen saturation.

^D CBC with differential includes: hemoglobin, RBC, platelets, MCV, WBC, absolute differential (neutrophils, lymphocytes, monocytes, eosinophils, and basophils). Local laboratory testing is permitted.

	Pre-Treatment Screening ^L	Cycle 1 ^M				Cycle 2 ^M				Cycle 3+ ^M				Off Study ^N
		Wk 1	Wk 2	Wk 3	Wk 4	Wk 1	Wk 2	Wk 3	Wk 4	Wk 1	Wk 2	Wk 3	Wk 4	
E	Serum chemistry must include: albumin, alkaline phosphatase, total bilirubin, bicarbonate, BUN, calcium, chloride, creatinine, glucose, magnesium, phosphorus, potassium, total protein, SGOT (AST), SGPT (ALT), sodium. Local laboratory testing is permitted.													
F	Coagulation factors include: aPTT, INR; required pre-study and as clinically indicated. Local laboratory testing is permitted.													
G	Serum or urine pregnancy test (for women of childbearing potential) must be completed at screening. If results are positive, the patient is ineligible and must be discontinued from the study.													
H	A 12-lead ECG is performed at screening and end of study. Additional ECGs are performed as clinically indicated.													
I	MRI or CT imaging to evaluate disease status is performed at baseline and once every 2 cycles (8 weeks) \pm 5 days. Imaging should be performed prior to the initiation of the next cycle of study treatment whenever possible.													
J	Pre-treatment biopsy is performed within 21 days of C1D1. The pre-treatment biopsy may only be collected after informed consent is obtained. On-study biopsy is performed on Day 3, 4, or 5 of cycle 2, 2-8 hours post-treatment with the study agents whenever possible. If the start of C2 is delayed, the biopsy should be delayed accordingly. The on-study biopsy should not be obtained if the patient has not begun dosing for C2.													
K	Blood collection for germline whole exome sequencing. Pre-treatment collection is performed within 21 days of C1D1. The pre-treatment research blood collection may only be collected after informed consent is obtained.													
L	All screening assessments must be performed within 21 days of C1D1.													
M	All assessments occur on day 1 of the specified week, unless otherwise noted. Start of cycle laboratory assessments may be performed up to 3 days prior to initiating treatment for a new cycle. Between cycle laboratory assessments may be performed \pm 3 days from the scheduled date. Local laboratory testing is permitted.													
N	Off-study evaluations must be performed within 21 days of the last dose of the study drug.													

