- 3.1.8 Patients with a history of hepatitis C virus (HCV) infection must have been treated and cured. For patients with HCV infection who are currently on treatment, they are eligible if they have an undetectable HCV viral load.
- 3.1.9 Patients with **treated brain metastases** are eligible if follow-up brain imaging after central nervous system (CNS)-directed therapy shows no evidence of progression, if patients have been clinically asymptomatic, and if patients have not received systemic corticosteroids for at least 28 days. Patients with brain metastases not meeting these criteria are not eligible.
- 3.1.10 Patients must be disease-free of prior invasive malignancies for >5 years, with the exception of curatively-treated basal cell or squamous cell carcinoma of the skin or

carcinoma *in situ* of the cervix.

NOTE: If there is a history of prior malignancy, patients must not be receiving other specific treatment for that cancer.

- 3.1.11 Patients with known history or current symptoms of cardiac disease, or history of treatment with cardiotoxic agents, should have a clinical risk assessment of cardiac function using the New York Heart Association Functional Classification. To be eligible for this trial, patients should be class 2B or better.
- 3.1.12 The effects of belinostat and SGI-110 (guadecitabine) or ASTX727 on the developing human fetus are unknown. For this reason, and because the DNA methyltransferase inhibitor decitabine, the active metabolite of SGI-110 (guadecitabine) and a component of ASTX727, is known to be teratogenic, and because belinostat may cause teratogenicity and/or embryo-fetal lethality by virtue of targeting actively dividing cells, women of child-bearing potential and men must agree to use adequate contraception (hormonal or barrier method of birth control; abstinence) prior to study entry and for the duration of study participation and for at least 6 months after the last dose of study drugs. Should a woman become pregnant or suspect she is pregnant while she or her partner is participating in this study, she should inform her treating physician immediately. Men treated or enrolled on this protocol must also agree to use adequate contraception prior to the study, for the duration of study participation, and 3 months after completion of belinostat and SGI-110 (guadecitabine) or ASTX727 administration.

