- 3.2.9 Pregnant women are excluded from this study because SGI-110 (guadecitabine) is a derivative of decitabine, and ASTX727 contains the agent decitabine, which has the potential for teratogenic or abortifacient effects, and because belinostat may cause teratogenicity and/or embryo-fetal lethality by virtue of targeting actively dividing cells. Because there is an unknown but potential risk for AEs in nursing infants secondary to treatment of the mother with SGI-110 (guadecitabine), ASTX727 and belinostat, breastfeeding should be discontinued.
- 3.2.10 Prolongation of the heart-rate corrected QT (QTc) interval ≥ 450 ms (*i.e.*, grade 1 or higher) on the screening electrocardiogram (ECG) prior to initiation of study treatment.

If baseline QTc on screening ECG is ≥ 450 ms (*i.e.*, grade 1 or higher):

- Check potassium and magnesium serum levels, and
- Correct any identified hypokalemia and/or hypomagnesemia and repeat ECG to confirm a QTc interval < 450 ms.

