4.4 General Guidelines

Following registration, patients should begin protocol treatment within 7 days. Issues that would cause treatment delays should be discussed with the Principal Investigator. If a patient does not receive protocol therapy following registration, the patient's registration on the study may be canceled. The Study Coordinator should be notified of cancellations as soon as possible.

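### The only pregnancy test required before dosing may be 21 days old at the first dose, and the calendar schedules no other until off-study

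*Combined protocol and SAP*

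**What the plan says.** **The exclusion and its reason.** Section 3.2.9 states: "Pregnant women are excluded from this study because SGI-110 (guadecitabine) is a derivative of decitabine, and ASTX727 contains the agent decitabine", and adds of decitabine "which has the potential for teratogenic or abortifacient effects". It gives a second reason: "belinostat may cause teratogenicity and/or embryo-fetal lethality by virtue of targeting actively dividing cells". Section 3.1.12 is firmer about decitabine: "the active metabolite of SGI-110 (guadecitabine) and a component of ASTX727, is known to be teratogenic".

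**The test.** The pregnancy-test row in the Section 11 calendar is marked at pre-treatment screening and at off-study. No column for cycle 1, 2 or 3+ is marked. Footnote G reads "Serum or urine pregnancy test (for women of childbearing potential) must be completed at screening" and makes a patient with a positive result ineligible. Footnote L sets the window: "All screening assessments must be performed within 21 days of C1D1". It gives no shorter limit for this test. Footnotes F and H provide for extra coagulation tests and ECGs when clinically indicated; footnote G has no such provision.

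**Laboratory work at cycle start.** CBC and serum chemistry are marked at week 1 of cycle 1. Footnote M, attached to the cycle headings, says: "Start of cycle laboratory assessments may be performed up to 3 days prior to initiating treatment for a new cycle".

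**Other safeguards.** Section 3.1.12 requires agreement to contraception before entry, during participation and for at least 6 months afterwards. Section 8.1.2 also requires contraception during ASTX727 treatment. Section 6.1 has the investigator see each patient on day 1 of every cycle. Section 6.3 tells women to report a suspected pregnancy at once and lists pregnancy among the reasons for ending treatment.

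**The concern.** The exclusion exists to prevent fetal exposure to agents that the protocol itself describes as harmful or possibly harmful. What matters for that purpose is the patient's status on the day exposure starts. The schedule establishes her status at some point in the preceding three weeks. A woman who conceives after a negative test on day -21, or whose pregnancy was too early to detect that day, reaches C1D1 with a compliant negative result. If the other safeguards do not raise a suspicion, nothing in the calendar calls for another test while she is on treatment.

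This is a gap between an eligibility criterion and the assessment schedule that supports it. No two passages contradict each other, and no efficacy or power figure is affected. It deserves raising because the harm would be serious and the remedy uses a laboratory visit that is already planned.

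**Working it through.** The plan states no figure on this point, so there is none to reproduce. The check sets the calendar row against its footnotes and then does date and count arithmetic.

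**1. Age of the result at first dose**
- Footnotes G and L: maximum age = 21 days.
- Section 4.4, "Following registration, patients should begin protocol treatment within 7 days", does not shorten this. Its clock starts at registration, not at the test.
- With a repeat in the footnote M window: maximum age = 3 days.
- Reduction: 21 - 3 = 18 days.

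**2. Interval between the two scheduled tests**
- Inputs: 21 days before C1D1 (footnote L); 28-day cycles with dosing on days 1-5, so the last dose falls 4 days after day 1 (footnote A); off-study evaluation up to 21 days after the last dose (footnote N).
- For k cycles without delay: longest gap = 21 + 28(k - 1) + 4 + 21 days.

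| Cycles given | Longest gap (days) | Scheduled tests in between |
|---|---|---|
| 1 | 21 + 0 + 4 + 21 = 46 | 0 |
| 2 | 21 + 28 + 4 + 21 = 74 | 0 |
| 4 | 21 + 84 + 4 + 21 = 130 | 0 |
| 6 | 21 + 140 + 4 + 21 = 186 | 0 |

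**3. Whether another provision supplies a test near C1D1**
- Contraception (3.1.12, 8.1.2): lowers the chance of conception; not a test.
- Day 1 visit with a limited, symptom-based examination (6.1, footnote B): may prompt a test; does not require one.
- Self-report (6.3): depends on the patient suspecting pregnancy.

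**4. Number of women concerned**
- Section 9 says 6 patients had been treated with SGI-110 at Amendment 5, and Section 6.1 closes that regimen to enrolment. A calendar change cannot help them. Section 9.5 puts the ASTX727 cohort at 13-26.
- Assumptions, not in the documents: half are women, and 20-50% of those are of childbearing potential.
- Full accrual: 26 x 0.5 = 13 women; 13 x 0.20 = 2.6 and 13 x 0.50 = 6.5, so about 3-7.
- Accrual stopped at 13: 13 x 0.5 = 6.5 women; 6.5 x 0.20 = 1.3 and 6.5 x 0.50 = 3.25, so about 1-3.
- The Section 9.5 enrolment table is not used for the sex split. Its row totals sum to 4 + 6 + 26 + 2 = 38 and its female columns to 17 + 2 = 19, against a printed total of 32.

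**The case against.** **The interval is already managed.** The contraception agreement starts before study entry, the investigator sees each patient on day 1 of every cycle, and nothing forbids a test when one is indicated. Section 6.3 speaks of a confirmed pregnancy, which presupposes testing on suspicion. This stands in part. A reader might infer from the calendar that the exclusion is not enforced at all, or that a pregnancy on study could come to light only if the patient reports it. The documents support neither. The exclusion is applied at screening, and the day 1 visits give a further chance to raise suspicion. What is missing is a scheduled test near first exposure.

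**The expected number of events is tiny.** Assume, purely for scale, a conception rate of 5-15% per year on contraception. Over the 18 days at full accrual this gives 2.6 x 0.05 x 18/365 = 0.006 to 6.5 x 0.15 x 18/365 = 0.05 conceptions. This stands, with one qualification: it leaves out pregnancies already present at screening but too early to detect, which a later repeat has a better chance of finding. A repeat can itself miss a very recent conception. The case rests on the severity of the harm and the low cost, not on frequency.

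**Why not simply move the one test to the days before C1D1, at no cost?** A reader might infer that this is enough. It would create other gaps. Section 4.3.1 requires eligibility to be verified before registration, and Section 4.4 lets registration precede treatment by up to 7 days. The mandatory research biopsy (5.1, footnote J) and baseline imaging (footnote I) also fall in the screening period. With only a late test, all three could go ahead without a pregnancy result. The screening test has to stay, so the repeat is an additional test.

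**Conclusion.** The point holds as a gap in the assessment schedule. The plan permits first exposure to a stated teratogen on a pregnancy result up to 21 days old, and it schedules no further test until off-study, a gap of up to 46 days for one cycle and 186 days for six without delays. These day counts follow directly from the footnotes.

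The number of women is small: about 3-7 at full accrual of the ASTX727 cohort, 1-3 if it stops at 13, and fewer if accrual is already advanced. Those counts rest on the assumed sex split and the assumed share of childbearing potential. They count women who would be retested, not missed pregnancies. A reader might take half of the 32 total, 16 women, as the base. The documents do not support that, because six of the 32 belong to the closed regimen and the enrolment table does not add up to its printed total.

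This is a worthwhile, inexpensive safety improvement. It has no bearing on the primary analysis.

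**What to change.** Reconcile Sections 3.2.9 and 6.3 with calendar footnotes G, L and M:

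- Keep the screening test, so that eligibility is verified before registration, biopsy and imaging.
- Mark a repeat test for women of childbearing potential with the cycle 1 start-of-cycle laboratory assessments, inside the existing footnote M window, and state in footnote G that the result must be known before the first dose.
- Leave any testing at later cycles to the study team.

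The edit is one calendar mark and one footnote. No dose, endpoint or sample size changes. The cost is one additional inexpensive test per woman of childbearing potential, done at a laboratory visit already planned, and an occasional late cancellation. If the repeat is positive, footnote G already makes the patient ineligible, and Section 4.4 already allows an untreated registration to be cancelled.
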